3.5.2. Inclusion/Exclusion

Participants must be 18 years of age or older and presenting for buprenorphine-naloxone treatment. Patients must be eligible to receive buprenorphine-naloxone medication (e.g., Suboxone, Bunavail, Zubsolv) during their visit at CAS. This study is open to all eligible participants.

Notably, due to the nature of medical treatment, approximately 5% of new patients will not follow the "regular" intake course of buprenorphine due to previous treatment and/or treatment initiation using injectable depot buprenorphine administration (which requires fewer physician visits). Because all patients initiating treatment are at risk for drop out/low adherence, we wish to enroll these participants if at all possible under the stringent timelines for this study. We will therefore enroll unusual buprenorphine-

naloxone initiation timelines on a case by case basis, dependent upon the ability to complete study procedures within the study timeline.

3.6. Cascade of Events

3.6.1. Baseline Visit

1. Explain study to participants to see if they are interested in participating
2. Obtain informed consent
3. Screening for inclusion/exclusion criteria
4. Complete baseline assessment questionnaires (20 minutes)
5. Measures of buprenorphine-naloxone dose prescribed at this visit will be acquired from the medical record
6. Randomization

3.6.2. Sessions 1-4: Intervention Treatment

- 1) Assessment questionnaires with interventionist
 - a) Assessment questionnaires completed (10 minutes)
- 2) Engage in either CM (2 minutes) or BSM (30 minutes)
 - a) BSM:
 - i) All BSM sessions will be audio-recorded in order for the study staff to evaluate treatment fidelity. Participants will be informed when the recording device is on, and permission to record will be obtained as soon as the recording device is started. Participants may refuse to have the session recorded and still participate. Audio recordings will be de-identified and labeled with a Study ID number stored on an encrypted computer.
 - b) CM:
 - i) A number wheel (pickerwheel.com) with varying levels of gift cards (ranging from \$25 to \$100) will be available.
 - ii) Urine toxicology will be obtained from the chart to assess presence of buprenorphine in urine (criteria for reward).
 - iii) Participants will be informed of the buprenorphine toxicology result.
 - (1) **IMPORTANT: IT IS BUPRENORPHINE IN URINE THAT RESULTS IN A GIFT CARD WIN.**
 - (2) **We ARE NOT providing feedback to the participant about the use of illicit substance presence in urine as this is not criteria for reward.**
- 3) Chart Review Following Intervention

- a) Information about buprenorphine-naloxone dose, all urine screen results (13 panel), and other substance use disorder diagnosis will be copied from the participant's medical chart.
- b) Opioid prescriptions will be obtained from prescription drug monitoring database.

3.6.3. Visit 4 ONLY: Follow-up Call (Blinded)

Assessments and treatment satisfaction questionnaire with Research Assistant blinded to treatment condition (25 minutes)

3.6.4. Final Chart Review

At 30 days following the last intervention visit, we will conduct a chart review to assess outcome data relevant to efficacy (attended medical treatment visit, buprenorphine in urine).

4.3. Investigator and Staff Responsibilities

4.3.1. Investigators

[name] will be responsible for the day-to-day supervision of the project and all aspects of the planning, training, recruitment, assessment procedures, and evaluation of the interventions in the proposed study. In collaboration with the research team, [name] will be responsible for decisions about the development of the study protocol, the training needed for the research staff who will be conducting the intervention, and interpretation of the data analysis and manuscript and presentation preparation.

[name] will assist with recruitment from UTHSC Center for Addiction Science and provide the medical care associated with the buprenorphine-naloxone medication.

[name] [name] will serve as the study physician for reporting of Adverse Events associated with the intervention, not the buprenorphine-naloxone medication. Dr.

[name] will assist with decisions about the development of study protocol, interpretation of the data, and manuscript preparation.

[name] will oversee data cleaning, including qualitative data, and conduct all quantitative analyses. He will assist [name] with the rational assignment of participant clauses in qualitative analyses. He will prepare results for publication and assist in manuscript development.

[name] will participate in intervention development and interventionist training. He will also conduct treatment fidelity on an ongoing basis.

[name] will conduct economic analyses of the intervention costs based upon efficacy.

[name] will assist with the development of recruitment sites and advise on study design.

[name] will advise the development of the mindfulness aspect of the intervention.

4.3.2. Project Manager

The Research Manager ([name]) will be responsible for general oversight of operational activities and supervision of personnel involved in data collection. She will be responsible for initial development of the MOP, development and maintenance of the database, exporting data and preparing for analysis. [name] will also prepare monthly reports on study progress for the investigative team.

The Research Project Coordinator will be responsible for direct staff supervision (coordinators, interventionists, and research assistants). The Project Coordinator will provide feedback on job performance and will conduct evaluations as per the requirements of UTHSC. The Project Coordinator will also be responsible for assigning additional tasks to staff as necessary to complete study goals.

4.3.3. Study Coordinator

The Lead Study Coordinator ([name]) will be responsible for study management tasks, including updating the Manual of Procedures, maintaining the regulatory binder (electronically), observing and reporting any study procedural issues to the study management, monitoring protocol adherence, ensuring data quality, reporting protocol deviations, completing IRB submissions/updates, developing consent forms, training staff, registering and updating the clinicaltrials.gov record, and relaying specific tasks to study staff members.

4.3.4. Interventionists

The Interventionists ([name] and [name]) will be responsible for participant and clinic relations including recruiting, consenting, and assessing participants. [name] and [name] will conduct BSM and CM intervention and will receive weekly supervision by Drs. [name] and [name].

4.3.5. Research Assistants

The Research Assistant will participate in recruiting, consenting, retention, blinded follow up assessments, and data abstraction.

4.4 Chain of Command

The Study Coordinator, Interventionists, and Research Assistant will report directly to the Project Coordinator regarding job responsibilities and duties. Should there be a conflict in reporting that requires the Study Coordinator, Interventionists, and Research Assistant to report to someone other than the Project Coordinator, the staff member will report to the Research Manager.

All Clinical Supervision will be provided by designated Investigators ([name] and [name]).

5. TRAINING PLAN

5.1. Pre-Initiation Training

All Clinical Research Staff will be trained in data collection, data entry, database use, informed consent procedures, protection of human subjects, good clinical practice, adverse event reporting, and administrative protocols (e.g., randomization, CAS procedures) by the Project Coordinator.

Interventionists will be trained by [name] to deliver the BSM intervention. The Study Coordinator will train the Research Assistant in chart review procedures.

5.2. Ongoing Training

Data will be monitored throughout the study so that any quality assurance issues can be handled in a timely manner. Any issues with data collection, data entry, informed consent, and incentive distribution will be monitored by [name] and the study coordinator and will be addressed at biweekly staff meetings. A log of data cleaning completions for staff will also be accessible in the study's OneDrive folder.

5.3. Clinical Training

Clinical supervision for Interventionists will be provided by Drs. [name] and [name]. This supervision will cover issues raised by fidelity checks, clinical training maintenance (e.g., practice of motivational interviewing techniques), and general evaluation of participants' progress. This is a good time for Interventionists to bring up clinical issues that have happened during the week, and for problem-solving how to interact with resistance participants.

5.4. Fidelity

All treatment sessions for Project 3 will be audio recorded. Fidelity for content will be conducted on 50% of all sessions (40 of a total 80 intervention sessions recorded) by [name]. Feedback regarding Interventionist performance will be provided by [name] and will be addressed in supervision.

6. RECRUITMENT PLAN

Recruitment will occur through the CAS clinic and the American Recovery Clinic (ARC). [name] and the other physicians at the clinic will be informed of the eligibility criteria so they can note potential participants. At each patient's visit, the physician will tell the new patient they may be eligible to participate in research that will assist them in adhering to buprenorphine treatment. The physician will make sure to explain that this is not required and is different from what they are receiving as standard treatment. If the patient expresses interest, the doctor will bring the patient to a research room where a research staff member will explain the study. The staff member will check for eligibility, and if eligible, consent the participant. Additionally, staff members may approach the physician or clinic staff in regard to determining some eligibility criteria for the patients after reviewing the clinic's schedule of appointments.

Please see the "Alternative Procedures: COVID" section if in-person recruitment is not possible.

7. ELIGIBILITY CRITERIA

Participants must meet the following eligibility criteria to participate in this study:

- Present for an appointment at CAS or ARC for buprenorphine-naloxone treatment of OUD
- Be eligible for buprenorphine-naloxone treatment (e.g., Suboxone, Bunavail, Zubsolv) as determined by [name]
- At least 18 years of age or older
- Access to a telephone
- Ability to understand consent procedures
- Physician confirmation of a "regular" initiation visit schedule (to ensure completion within pilot study window)

8. PROCEDURES

8.1. Recruitment

Recruitment will occur through the CAS and ARC clinics. Potential participants will be identified from the appointment schedule at the beginning of each day by [name] or the attending physician. At each patient's visit, the physician will tell the patient they may be eligible to participate in research. The physician will make sure to explain that this is not required and is different from what they are receiving as standard treatment. If the patient expresses interest, the doctor will bring the patient to a research room where a research staff member will meet with the participant. The study will be explained to the participant using the consent statement. Additionally, staff members may approach the physician or clinic staff in regard to determining some eligibility criteria for the patients after reviewing the clinic's schedule of appointments.

8.2. Enrollment

8.2.1. Consent

Project staff will answer any questions about the entire process and an informed consent will be obtained. No study assessment will take place prior to obtaining consent from each subject. Standard language in our consent form assures the participants of the confidential nature of the study and the ability to withdraw from the study at any time. The consent forms will contain HIPAA language. This study will be approved by the UTHSC IRB.

Participants will be given a copy of the consent statement for their records. The consent discussion will be documented on the eligibility page of the FileMaker Database.

Participants will be informed that regardless of their adherence to clinic visits or use of buprenorphine-naloxone (the primary study outcome), they will be eligible to complete assessments at scheduled intervals and will be compensated for these assessments. This will enable the study team to discover whether drop out of treatment leads to relapse to opioids and if treatment is sought elsewhere.

8.2.2. Baseline Visit

After consent, the participant will complete the baseline assessments with the study team member. Dependent upon COVID-19 County and UTHSC requirements for in-person assessments, participants will either fill out paper forms on their own or be interviewed by the staff member. Responses will be recorded in the FileMaker database.

If a participant is unable to complete their baseline assessment on the day of enrollment, that is ok. Assessments may also be completed over the phone. Assessments however, must be finished before Visit 1.

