3.4. Duration

3.4.1. CM Group Course and Session Duration

Participants assigned to the CM arm will have contact with study staff at their first physician visit (intake visit at the Center for Addiction Science) and then at the following 4 physician visits that are scheduled as a regular buprenorphine-naloxone treatment course. These visits are often scheduled at 1 week, 2 weeks, 4 weeks, and 8 weeks following intake (see Figure 1). However, this varies with some patients, thus participation could potentially last 4 months as a result of them being seen on a monthly basis. Participation at each intervention session is expected to last for 10minutes for the assessment and 2 minutes for the intervention (“number wheel” gift card picker).

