10. ALTERNATIVE PROCEDURES: COVID

In the case that study staff are unable to recruit and provide the intervention in-person, the following alternative procedures will take place.

All individuals entering the CAS must abide by the rule of wearing a face mask at all times.

Procedures

Recruitment

Study staff will review the clinic schedule the day before and the day of to determine which patients are eligible. Study staff will come into the clinic to discuss the study and recruit eligible patients.

Enrollment

Consent

If the patient agrees to participate, the study staff will consent in person. The study team will take all precautions to protect themselves and the patient (e.g., PPE and practice social distancing).

For participants unable to complete consent in person and who have access to a computer, a DocuSign link will be sent immediately to conduct consent during the call. A blank copy of the consent form will be mailed to the participant

All other consent procedures will be the same as written above.

Randomization

Once the patient consents and completes baseline assessments, randomization procedures will stay the same as written above.

Baseline Assessment

Baseline assessment will take place in-person or over the telephone. Assessment must be completed prior to the participant's first physician return visit. Procedure will stay the same as written above.

Sessions 1-4

Following the Baseline Visit (BV), participants will complete sessions on the same schedule as their appointments at CAS, but windows will not exceed 30-day increments. Sessions and follow-up procedures will stay the same as written above with a few modifications (see below).

CM Session

Study staff will contact participants by phone or text to schedule a time to complete their assessment and CM intervention via Zoom call on the day of the participants' scheduled appointment. The participant will be given a 30-day window (starting with the day of their office visit) to complete the assessment or it must be completed prior to the next scheduled clinic visit for the patient.

If participant attends the physician appointment **and** has buprenorphine in urine:

Once the assessment is complete, the study staff will spin the number wheel while the participant is on the phone ("virtual wheel"). The study staff will inform the participant of the gift card amount earned and will immediately mail the gift card.

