12.2.23. PEG for Chronic pain (3 items)

	0 No Pain	1	2	3	4	5	6	7	8	9	10 Pain as bad as you can imagine
What number best describes your pain on average in the past week?	0 No Pain	1	2	3	4	5	6	7	8	9	10 Pain as bad as you can imagine
What number best describes how, during the past week, pain has interfered with your enjoyment of life?	0 No Interference with Enjoyment	1	2	3	4	5	6	7	8	9	10 Completely Interfered with Enjoyment
What number best describes how, during the past week, pain has interfered with your general activity?	0 No Interference with Activity	1	2	3	4	5	6	7	8	9	10 Completely Interfered with Activity

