14. VIRTUAL MAILING PROCEDURES

Session /Mailing Procedures:

Baseline

- If participant completes the full package in-person, they will receive a \$50 gift card before they leave the clinic.
 - Each interventionist is responsible for taking care of their own gift cards and welcome package (T-shirt, copy of consent, SOBER handout [BSM group only], and business card).

Instructions:

- Log gift cards out of the safe.
- Complete the GC sheet and make copy of gift card for study records.
 - Ppt. will need to sign off on the sheet. Once completed place in GC binder.
- Present GC to ppt
- Welcome ppt. to the study and hand them their welcome bag.
- Schedule next session (based on their appt. with clinic).

- If the participant takes the packet home, they will need to return the package back or call to complete the assessment over the phone. Once completed, we will mail them a \$50 gift card; if they come back into the clinic, we will give them a gift card in person.
 - Each interventionist is responsible for taking care of their own gift cards and welcome package (T-shirt, copy of consent, SOBER handout [BSM group only], and business card).

Instructions:

- Schedule a time to complete baseline.
 - Inform the ppt. that we will not be able to mail GC without completing the pack first.
- Welcome ppt. to the study and hand them their welcome bag.
 - T-shirt, copy of consent, SOBER handout [BSM group only], and contact card.
 - No GC will be given until pack is completed.

Once baseline is completed:

- Log gift cards out of the safe.
- Complete the GC sheet and make copy of gift card for study records.
 - Once completed place sheet in GC binder (ppt. will not need to sign).
- Mail GC to ppt.

- Mail can be dropped off at the UCH lobby or nearest postal office.
- Use SMART mailer and envelop.

Sessions 1-3 (Virtual)

- After the participant completes all the assessments and the intervention, they will receive their GC. Appointments will be scheduled within 30 day windows.

- **CM Group Instructions:**

- Complete assessments
- Inform ppt. of the GC amount they will receive, and to please allow 2-3 business days to arrive.
 - \$50 for completing assessments.
 - Additional GC will depend on the following:

Urine toxicology results

- If participant is compliant, buprenorphine in their urine, we will spin the virtual wheel for them and inform them of the amount received.

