Statistical Analysis Plan: SMART Project 3 (Efficacy Study)

Because these analyses will focus on determining and intervention feasibility and satisfaction, and preliminary intervention effect sizes (with less concern focused on testing for statistical significance), outcome analyses will be conducted using a separate analysis for each outcome at each follow up observation. To compare groups, baseline and follow up variables will be entered into a 5 (baseline vs. follow ups at 1, 2, 3, and 4 weeks) by 2 (CM vs. BSM) analysis of variance (ANOVA) which will yield effect sizes for time, and interactions of time by intervention. The primary dependent variables will be attendance at physician visits, saliva drug screen data (positive for buprenorphine and negative for illicit opioids), and prescription drug monitoring. We hypothesize that a greater number of CM participants will demonstrate adherence to buprenorphine-naloxone than BSM, but that those randomized to BSM will report increased time allocated to substance-free activities, decreased delayed reward discounting, and demand for opioid.

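### Baseline may be completed up to the first return visit, after medication is prescribed at intake, so late self-report baselines are partly or wholly post-prescription and blur the SAP's time effects

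*Protocol*

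**What the plan says.** Same-day completion is the default sequence in Protocol 3.6.1, but three places allow a later baseline.

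- Protocol 8.2.2: "If a participant is unable to complete their baseline assessment on the day of enrollment, that is ok". The phone may be used, and the limit is "Assessments however, must be finished before Visit 1".
- Protocol section 10 (COVID procedures): "Assessment must be completed prior to the participant's first physician return visit".
- Protocol section 14: "If the participant takes the packet home, they will need to return the package back or call to complete the assessment over the phone".

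The participant withdrawal section mentions a designated window for baseline but gives no tighter limit.

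The prescription belongs to the same visit. Protocol 3.6.1 lists "Measures of buprenorphine-naloxone dose prescribed at this visit will be acquired from the medical record". On the return visits, 3.4.1 says: "These visits are often scheduled at 1 week, 2 weeks, 4 weeks, and 8 weeks following intake".

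The recall items run back from the day the form is filled in. PEG, for example, asks "What number best describes your pain on average in the past week". Craving item 2 also asks about the past week, and PHQ-2 and GAD-2 ask about two weeks. The timeline followback is headed by the current date and has seven day columns. Craving items 1 and 3, the Opioid Purchase Task and delay discounting ask about the respondent's present state or choices.

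The SAP enters baseline as the first of five time levels in an "analysis of variance (ANOVA) which will yield effect sizes for time, and interactions of time by intervention". Neither document ties a late baseline to the intake date, uses its lag, or plans a sensitivity analysis for it.

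**The concern.** A time effect measured from baseline is meant to show change from the state before treatment. If some participants supply their starting value several days after the prescription, that level mixes two states. Any early change in craving, use or opioid demand is then understated, and participants whose lags differ are treated as if measured at the same point. The baseline also becomes noisier if it is used in the time-by-arm comparison.

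This matters here because the SAP says its interest is in preliminary effect sizes more than in significance. Two self-reports named in its hypotheses, opioid demand and delay discounting, are exposed. With about 40 participants, each late completer is 1/40 = 2.5% of the sample.

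**Working it through.** The documents give no figure on this point to reproduce, so the check is a count of days.

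**Inputs.** Intake and prescription are day 0 (Protocol 3.6.1). Baseline is completed on day d, before Session 1 on day s (8.2.2, section 10). The usual s is 7 (3.4.1). Recall length R is 7 days for PEG and craving item 2, and 14 for PHQ-2 and GAD-2. The timeline followback is taken as R = 7. That is a reading of its layout, because the form does not say which seven days are meant.

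**Formulas.** A recall of R days completed on day t covers days t − R to t − 1.
- Post-prescription days in the baseline recall = min(d, R).
- Days shared with the Session 1 recall = max(0, R − (s − d)).

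**Usual schedule, s = 7.**

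| Baseline day d | Post-prescription days, R = 7 | Shared with Session 1, R = 7 | Post-prescription days, R = 14 | Shared with Session 1, R = 14 |
|---|---|---|---|---|
| 0 | 0 | 0 | 0 | 7 |
| 1 | 1 | 1 | 1 | 8 |
| 3 | 3 | 3 | 3 | 10 |
| 6 | 6 | 6 | 6 | 13 |

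As an example, a 7-day recall on day 6 covers days −1 to 5 and Session 1 covers days 0 to 6. They share days 0 to 5, which is 6/7 = 86%. On day 1 the share is 1/7 = 14%, and on day 3 it is 3/7 = 43%. PHQ-2 and GAD-2 share 7 of 14 days even when baseline is on time, so that part is not caused by lateness.

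**Longer gaps (assumed s).** With s = 14 and R = 7, a day-6 baseline has 6 post-prescription days and no shared days; a day-13 baseline has 7 and 6. With s = 30, a day-29 baseline is wholly post-prescription: 7 of 7 days with 6 shared, or 14 of 14 with 13 shared.

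**Which outcomes.** By Table 1, the Opioid Purchase Task is given at baseline and at every session. Delay discounting is given at baseline and the 8-week blinded call. Neither has a recall window, so for a late completer the whole value is post-prescription, but the overlap count does not apply to them.

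**Effect on the time estimate.** Let f be the share of late baselines. The documents do not give it, so 10% to 50% is assumed for illustration.
- Current-state items: if late completers have already made all of the early change, the mean baseline-to-Session 1 change shrinks by f, that is by 10% to 50%. If they have made only part of it, it shrinks by less.
- Seven-day items, with k post-prescription days and each day weighted equally: shrinkage = f × k/7. For k = 6 this is 0.10 × 6/7 = 9% to 0.50 × 6/7 = 43%. For k = 1 it is 0.10 × 1/7 = 1% to 0.50 × 1/7 = 7%.

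These are upper-end illustrations, not estimates.

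**Order of baseline and randomisation.** Protocol 8.2.3 randomises only after baseline is complete, and section 10 keeps that order. Section 14 has staff give the take-home participant a welcome bag before the packet is finished, and the bag contains a handout for the BSM group only. Both cannot hold for the same participant.

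**The case against.** The strongest reply is that little of consequence is touched. The primary outcomes in Protocol 3.3 are feasibility, satisfaction, and attendance with urine buprenorphine. Attendance and urine results come from the chart, and none of the three depends on the self-report baseline. The SAP does not name craving, pain, PHQ-2, GAD-2 or timeline followback; they enter only as unspecified baseline and follow-up variables. The medication is background care, and the randomised interventions start after intake. All of this stands and limits the point to the time effects of self-reports.

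A reader might infer three stronger things that the documents do not support.

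- That baseline largely duplicates Session 1. The 86% overlap is the last possible day on a one-week schedule, and it applies to no outcome that the SAP names.
- That late completers are already taking the medication. The documents place the prescription at intake but do not state when the first dose is taken, and 3.5.2 notes previous treatment in some patients. Post-prescription is as far as the text goes.
- That the arm comparison is biased. If 8.2.3 is followed, the arm is unknown when baseline is completed and lag cannot depend on it. Section 14 puts this in doubt but does not show that it fails.

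It is also fair to object to rewording PEG, PHQ-2 and GAD-2. They have fixed recall periods, and section 12.2 says that some items are funder requirements. Their wording is better left alone.

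**Conclusion.** The point holds as a limited one. As written, the plan lets post-prescription values enter the starting level of the self-report time effects, and nothing in the analysis detects or adjusts for it. The named outcomes exposed are opioid demand and delay discounting; the craving items and the recall measures are exposed as well. On the usual schedule the contamination of a 7-day item runs from 1 to 6 of 7 days, and it can be complete if the first return visit is later.

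The size of the effect on the estimates cannot be computed because the share of late baselines is unknown. Chart-based attendance and urine buprenorphine are untouched. The absence of average arm bias rests on 8.2.3 being followed, so its conflict with section 14 needs resolving. This is a worthwhile, inexpensive improvement and not a flaw that threatens the trial's main conclusions.

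**What to change.** In Protocol 8.2.2 and section 10:

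1. Take the Opioid Purchase Task (1 minute), delay discounting (2 minutes) and the Opioid Cravings Scale (1 minute) on the intake day, even when the rest of the packet is deferred. By Table 1 that is 1 + 2 + 1 = 4 minutes.
2. State that the baseline timeline followback covers the 7 days before intake. Its post-prescription days, and its overlap with a day-7 Session 1, then fall to 0.
3. Leave PEG, PHQ-2 and GAD-2 wording unchanged.
4. Record the completion date and the lag from intake for the whole baseline. The followback form already has a date field.

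In the SAP, repeat the time-effect estimates excluding self-report values taken after the intake day, and report how many were excluded. This covers the deferred measures that keep their wording. It does not remove the 7 of 14 days that on-time PHQ-2 and GAD-2 share with a day-7 Session 1.

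Reconcile 8.2.3 with section 14 on whether the arm can be known before a take-home baseline is complete.

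Cost: about 4 minutes at intake, one sensitivity analysis, and up to about a week of extra recall on one form for late completers on the usual schedule (longer if the first return visit is later).
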